13.1.5.1. Model Checking & Diagnostics

As an initial model fit 100,000 MCMC samples will be generated with a thin of 10, providing 10,000 samples to be used for the estimate of the posterior distribution. A burnin of 5,000 samples will be used. Starting values for the parameters will be based on the mode of the prior distributions.

The following list of convergence diagnostics will be applied for each parameter (diagnostic checking outputs will be stored in the refdata folder in HARP in the relevant reporting effort):

- The Monte Carlo Standard Errors (MCSE) should be compared with the standard deviation of the posterior distribution (SD) to ensure that only a fraction of the posterior variability is due to the simulation. The number of samples generated, and/or the thinning may be increased to reduce the ratio of the MCSE/SD as deemed necessary.
- Trace plots of samples versus the simulation index will be visually inspected to assess some aspects of convergence. The centre of the chain should appear stable with very small fluctuations, i.e., the distribution of points should not change as the chain progresses and the posterior mean and variance are relatively constant.
- Autocorrelation plots will be visually inspected to assess degree of autocorrelation (should decline rapidly and show no oscillation patterns).
- Density plots of the posterior for the model parameters will be plotted (should be smooth and with a single hump).

If the model is not deemed to have converged the following actions will be taken in the order described below:

- Increasing the number of MCMC samples and/or the thinning will be explored. The blocking of the parameters will be considered.
- For the joint model:
 - \circ The variance of the parameters used to model the baseline data may be considered as fixed, based on the observed variance of the parameter rather than using δ_i ~iGamma(shape=0.1, scale=0.1).
 - The endpoint with the most missing data will be removed from the model and the joint model carried out on the remaining 3 endpoints.
- For the MMRM model:
 - If missing data at the post-treatment visits are causing the nonconvergence, these visits will be removed and details included in a footnote.

201247 | Statistical Analysis Plan RAP Amendment 3 Final_V1 21 Aug 2020 | TMF-2068612 | 1.0

CONFIDENTIAL

201247

• Removal of covariates will be considered, starting with MMF use at day1, then the baseline by visit interaction (if applicable).

After which if the model still does not converge, the model results will not be presented.

13.2. Exploratory Biomarker Analyses

13.2.1. Mechanistic Haematology

Note that the exploratory endpoints that are categorised as 'blood biomarkers related to mechanisms of anaemia and thrombocytopenia' in the protocol are categorised as 'Group 2 – Mechanistic Haematology/chemistry' in Section 7.2. Reporting of these parameters will use the same outputs as other Haematology/ chemistry but will only occur at the end of the study. See Appendix 12. No statistical analysis will be performed on these endpoints. These displays will use the 'Safety' population unless otherwise specified.

201247

14. EFFICACY ANALYSES

Exploratory biomarker analysis will take place at the final SAC.

14.1. Exploratory Efficacy Analyses

14.1.1. Endpoint / Variables

The analyses of clinical disease assessments (preliminary assessment of efficacy in Systemic Sclerosis) will be based on the Per Protocol population, unless otherwise specified. They will consist of the following endpoints:

- mRSS
- HAQ-DI
- SHAQ VAS scales
- PhGA
- PtGA
- CRISS (derived non-parametric summaries)
- Laboratory FVC (L) (Note: impact of treatment on the rate of change will be inferred from the Figures)
- % predicted laboratory FVC
- Weekly Home FVC (L) (Note: impact of treatment on the rate of change will be inferred from the Figures)

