
 To explore the PK and target engagement of repeat subcutaneous doses of GSK2330811 in the skin of participants with dcSSc using suction induced blisters 	
 Endpoints may include (but are not limited to): 
 Levels of GSK2330811 in blister fluid measured anytime between Day 57 and Day 85 (Week 8 and Week 12) Levels of OSM in blister fluid measured anytime between Day 57 and Day 85 (Week 8 and Week 12)

 To explore the effect of repeat subcutaneous doses of GSK2330811 on the extent of skin involvement in participants with dcSSc 	
 Change from baseline in modified Rodnan skin score (mRSS) over time

 To explore the effect of repeat subcutaneous doses of GSK2330811 on lung function in participants with dcSSc 	
 Rate of change in forced vital capacity (FVC) Change from baseline in FVC

 To explore the effect of repeat subcutaneous doses of GSK2330811 on SSc related symptoms, physical function and disease activity in participants with dcSSc 	
 Change from baseline in Scleroderma Health Assessment Questionnaire (SHAQ) Change from baseline in Physician Global Assessment of Disease Activity (PhGA) Change from baseline in Patient Global Assessment of Disease Activity (PtGA) Composite Response Index for Systemic Sclerosis (CRISS)

Objectives	Endpoints

 To characterise the mechanisms of any observed haematological effects of GSK2330811. 	
 Change from baseline in selected blood markers related to mechanisms of anaemia and thrombocytopenia.

[figure not shown]

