Information collected during the screening assessments described below represents key data that identifies and defines the participant's status.

Informed Consent: Informed consent will be obtained from the participant prior to initiation of any study procedures or study-specific data collection.

During the screening period screening assessments will be performed as outlined in the Section 2 and include:

Demographic parameters: Will be captured: year of birth, sex, race and ethnicity.

Medical history: Will be assessed as related to the inclusion/exclusion criteria listed in Section 6 (as detailed in the eCRF).

Respiratory Tests:

1. Respiratory Laboratory Tests (FVC and DLCO) for Eligibility.

Hospital based lung function equipment will be used to measure lung function tests and be overseen by a respiratory physiologist. Lung function tests will be recorded whilst the participant is in a sitting position (if taken whilst the participant is on the bed, their legs should be over the edge) and may be repeated, until technically acceptable measurements have been made. The respiratory laboratory measured FVC and DLCO will be recorded in the eCRF.

2. Home Spirometry (FVC).

The rate of decline in daily FVC, measured at home via a hand held spirometer, in patients with IPF has been shown to be highly predictive of outcome and subsequent mortality (Russell, 2016). Training on use of the hand held spirometer will be given during the screening visit and a refresher course offered at Day 1. After initial training, three FVC readings will be obtained and recorded by the participant at the first screening visit. The participant will then continue to measure weekly FVC on a day convenient to them throughout the screening period and until the end of the study. The participant will enter the readings into their paper diary. The paper diary entries will be transcribed into the eCRF.

Baseline Assessments taken at Day 1 only

Autoantibodies: To aid patient characterisation and potential future stratification a blood sample will be taken on Day 1 for assessment of autoantibody status, including but not limited to Anti-Scl-70, Anti-centromere and Anti-RNAPIII.

Medical History: Medical history will include SSc-related factors, smoking and cardiovascular medical history / risk factors and information from the participant's most recent lung HRCT scan, if available, as detailed in the eCRF.

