Non-informative priors will be used in these analyses, specifically the prior for the regression coefficient will be normally distributed with mean 0 and a variance of 10^6 . The prior for the variance parameter will be an inverse-gamma (shape=0.001, scale=0.001).

The models will be adjusted for the following covariates: MMF use at day 1, baseline value and treatment.

Nature of Data	Output Presentation
Log Transformation	 The change from baseline and difference in the treatment groups (GSK2330811 300mg – placebo) will be back transformed to give ratio to baseline and ratio of the change relative to placebo respectively. Posterior medians, equal tailed 95% credible intervals, probability that ratios < 1 and fold change (i.e., Posterior Medians, as ratio < 1 then fold change is -1/ratio otherwise fold change is ratio) will be presented.
Linear	 Change from baseline and the difference in the treatment groups (GSK2330811 300mg – placebo) will be calculated. Posterior medians and equal tailed 95% credible intervals will be presented. Except for Downregulated GSVA score, the probability that difference < 0 will be calculated. For Downregulated GSVA score, the probability > 0 will be calculated.
201247

The plot of the adjusted posterior medians \pm credible intervals along with individual ratio to baseline or change from baseline values based on the endpoints will be presented.

Joint model

In addition to the Bayesian MMRM analysis, the ratio to baseline or change from baseline based on the endpoints for the following four key biomarkers will be modelled using a multivariate Bayesian analysis including only the placebo and GSK2330811 300mg arms:

- Alpha SMA (Excluding Insufficient samples)
- CCL2 gene assessed from the skin sample through RNA sequencing
- PIIINP assessed from the serum sample
- 2GSSc

Non-informative priors will be used for all parameters. The variance-covariance matrix for the within subject error across the endpoints will use an inverse-Wishart prior distribution consisting of the identity matrix and 4 degrees of freedom.

The model will be adjusted for endpoint (allows each endpoint to have their own intercept), treatment by endpoint interaction term, MMF use at day 1 by endpoint interaction, and baseline by endpoint interaction term. If the model does not converge, the covariate for MMF use will be removed from the model.

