14.1.2. Summary Measure

Summary statistics for all endpoints listed in Section 14.1.1 will be presented by visit and for the change from baseline at each visit. Line plots of unadjusted means \pm standard error at each visit and individual participant plots of the raw values will be presented by treatment groups and individual plot lines are differentiated by MMF use at Day 1 (solid line denote subjects on mycophenolate at day 1 and dashed line denote subjects not in mycophenolate at day 1). Information on positive autoantibodies is added to the subject ids in the legend as per Section 6.1.

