14.1.5. Statistical Analyses / Methods

Details of the planned displays are provided in Appendix 12 and will be based on GSK Data Standards and statistical principles.

201247

The endpoints / variables defined in Section 14.1.1 will be summarised using descriptive statistics, graphically presented (where appropriate) and listed.

Longitudinal model

Longitudinal Bayesian model as specified in Section 13.1.5 will be fitted for the change from baseline in the following endpoints:

- mRSS
- HAQ-DI
- Laboratory FVC (L)

The difference in the differences from baseline will be calculated across the treatment groups (GSK2330811 300mg – placebo).

Posterior means and equal tailed 95% credible intervals will be presented. In addition, except for Laboratory FVC, the probability the differences are <0 will be calculated and for Laboratory FVC, differences are >0 will be calculated. The line plots of the adjusted posterior mean change from baseline \pm credible intervals at each visit will be presented.

Non-Parametric Analysis

The CRISS endpoint is not expected to be normally distributed and so will be analysed using Bayesian non-parametric techniques including only placebo and GSK2330811 300mg arms.

Observed data from two groups are assumed to come from an underlying latent normal distributions with unit variance. Observations from these two latent normal distributions are generated from the truncated normal distributions in such a way to maintain the ordinality of the data. The parameter of interest is difference in the two latent means, δ . Prior distribution of δ , will be Cauchy distribution with shape parameter 0.5 and scale parameter $1/\sqrt{2}$. To obtain the posterior distribution for δ , analysis will follow the algorithm advocated by van Doorn, 2020.

Probability difference > 0 will be presented.

Boxplots of the predicted probability of improvement from baseline in the CRISS endpoints at day 85 and day 197 will be presented by treatment group.

Correlation Analysis

In addition, correlation analysis will be performed at Day 85 for set of endpoints listed below. The correlation will be presented as scatter plots of endpoints for each of the treatment groups, including the Pearson correlation coefficient. For ratios, correlations will use the log transformed data while the plot will present the untransformed data with the appropriate axis presented on the log scale.

- For each combination of change or ratio of key biomarkers

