9.21	Per Protocol	EFF_T1	Summary of Weekly Home FVC (L)		SAC		
9.22	Per Protocol	EFF_T1	Summary of Change from Baseline in Weekly Home FVC (L)		SAC		

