9.20	Per Protocol	BIO_F4	Individual Subject Profiles for Weekly Home FVC (L) by Treatment Group		SAC	
Correlat	ion Analysis					
9.21	Per Protocol	EFF_F4	Correlation of Change in FVC vs Biomarker Endpoints		SAC	
9.22	Per Protocol	EFF_F4	Correlation of Change in mRSS vs Biomarker Endpoints	Panel by treatment group and grouped	SAC	
9.23	Per Protocol	EFF_F4	Correlation of Baseline OSM (Skin) vs Biomarker Endpoints and Change in mRSS	by individual subjects	SAC	
Notes: 1: reduce th	Individual figur	e(s) will be produce blinding, so this out	ed for interim but may not be shared. Justification: DRCs follow the put will only be presented if necessary.	principle of presenting summary data w	nere possible to	

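### For weekly home FVC the SAP plans no between-arm estimate of rate of change: the treatment effect is to be read from figures, and the mean plots carry no error bars.

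*SAP*

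**What the plan says.** - **Endpoint.** Protocol section 4 and SAP 2.2 name two exploratory FVC endpoints: a rate of change and a change from baseline. Protocol 10.3.1 leaves exploratory methods to the RAP, so the SAP is where a rate analysis would appear.
- **Reason for home spirometry.** Protocol section 9 introduces it with a finding on rate: "The rate of decline in daily FVC, measured at home via a hand held spirometer, in patients with IPF" is said to predict outcome. Participants then record readings weekly until Day 197.
- **Method.** SAP 14.1.1 attaches the same note to laboratory FVC and to weekly home FVC: "impact of treatment on the rate of change will be inferred from the Figures". SAP 2.4.4 states that exploratory efficacy will be approached by Bayesian estimation.
- **Models.** SAP 14.1.5: "Longitudinal Bayesian model as specified in Section 13.1.5 will be fitted for the change from baseline in the following endpoints", namely mRSS, HAQ-DI and laboratory FVC in litres. Time enters through visit and treatment-by-visit terms. No slope is defined, and home FVC is not in the list.
- **Displays.** SAP 14.1.2 sets the general rule for the 14.1.1 endpoints: "Line plots of unadjusted means" with standard errors. In SAP 16.12.19 the programming note for Figures 9.18 and 9.19 (home FVC and its change from baseline) calls for no error bars. Home FVC also has descriptive Tables 9.21 and 9.22 and Figure 9.20, "Individual Subject Profiles for Weekly Home FVC (L) by Treatment Group".

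**The concern.** Impact of treatment is a between-arm statement. For home FVC the plan offers only two mean lines without uncertainty, plus descriptive tables and individual profiles. Nothing in Appendix 12 reports a difference in rate between 300 mg and placebo.

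Home FVC is also the more natural source for a rate. Weekly readings from Day 1 to Day 197 give up to 29 nominal points per participant, against three laboratory visits (Days 1, 85 and 197).

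With few placebo participants, two lines can separate visibly by chance. The clinical study report could then describe a slower decline on active treatment, or none, on visual impression alone. What is at stake is the reading of one exploratory endpoint.

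**Working it through.** The documents give no SD, target or precision for FVC, so there is no plan figure to reproduce for this endpoint. As a check on the interval formula only, the protocol's PIIINP precision (section 10.1: SD 0.521, 15 vs 5) comes back as t(0.975, 18) × 0.521 × √(1/15 + 1/5) = 0.565, as stated there.

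**Step 1: what is planned for each FVC source**

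| | Laboratory FVC | Weekly home FVC |
|---|---|---|
| Effect on rate (14.1.1) | From figures | From figures |
| Between-arm model (14.1.5) | Change from baseline, 95% credible interval, P(>0) | None |
| Mean plot | 9.4: mean ± SE | 9.18, 9.19: no error bars |
| Within-arm spread | Tables 9.4, 9.5; Figure 9.6 | Tables 9.21, 9.22; Figure 9.20 |

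**Step 2: group sizes**

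Protocol 10.1 gives cohort 2 as 20 to 36 participants at 3:1, that is 15 vs 5 to 27 vs 9. Cohort 1 starts with four participants at 3:1, so one is on placebo. SAP 5.1 has a single Placebo group, and the models in 13.1.5 use it without limiting it to cohort 2. The comparison of 300 mg with placebo is therefore about 15 vs 6 to 27 vs 10.

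**Step 3: separation by chance**

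Assumptions, not from the documents: SD of 12-week home-FVC change 0.15 to 0.30 L; a visible gap of 0.10 L; no true effect; normal means.

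SE = SD × √(1/n1 + 1/n2), and P = 2 × [1 − Φ(0.10/SE)].

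| n | SD (L) | SE (L) | 0.10/SE | P(gap ≥ 0.10 L) |
|---|---|---|---|---|
| 15 vs 6 | 0.15 | 0.072 | 1.38 | 17% |
| 15 vs 6 | 0.30 | 0.145 | 0.69 | 49% |
| 27 vs 10 | 0.15 | 0.056 | 1.80 | 7% |
| 27 vs 10 | 0.30 | 0.111 | 0.90 | 37% |

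**Step 4: what a slope estimate would deliver**

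Take 13 weekly points, weeks 0 to 12. The sum of squared deviations from week 6 is 182, so a fitted 12-week change has error variance (144/182)s² = 0.791s², where s is the SD of a single home reading. With τ the between-person SD of true 12-week change,

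half-width = t(0.975, N − 4) × √(1/n1 + 1/n2) × √(τ² + 0.791s²).

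Assumed ranges: s from 0.10 to 0.20 L, τ from 0.05 to 0.20 L. The root term then runs from √(0.0025 + 0.0079) = 0.102 to √(0.0400 + 0.0316) = 0.268.

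- 15 vs 6: 2.110 × 0.483 × (0.102 to 0.268) = 0.10 to 0.27 L per 12 weeks.
- 27 vs 10: 2.035 × 0.370 × (0.102 to 0.268) = 0.08 to 0.20 L per 12 weeks.

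These assume complete weekly data. Missing readings and Per Protocol exclusions would widen them. Least squares stands in for the vague-prior Bayesian fit.

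**The case against.** The strongest reply is that this is a disclosed choice in a small, short study. Protocol 3.1 says no formal hypothesis will be tested, and the SAP openly states how the rate will be judged. Several other exploratory measures (SHAQ VAS scales, PhGA, PtGA, percent predicted FVC) are also left descriptive. The figure-level instruction can be read as a deliberate exception to 14.1.2, since error bars at up to 29 weekly points would crowd the plot. The cited rationale concerns daily readings in IPF, whereas here readings are weekly, self-measured and kept in a paper diary in dcSSc. It explains the device and does not commit the trial to a slope analysis.

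Much of that stands, and it is why the point is minor. It does not remove the gap. Home FVC differs from the other descriptive endpoints because the SAP says a treatment impact will be inferred from it, and the mean plots meant for that inference are the ones without uncertainty. Crowding can be handled by layout.

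A reader might infer something stronger: that the FVC rate endpoint as a whole has no estimate behind it. The documents do not support that. Laboratory FVC change from baseline is compared between arms at fixed visits with a credible interval. Divided by elapsed time, that difference is an average rate, though the SAP does not label it so. Nor is spread in home FVC hidden, since Tables 9.21 and 9.22 and Figure 9.20 show it within each arm.

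**Conclusion.** The point holds for weekly home FVC only. The SAP intends a between-arm inference about its rate of change but specifies no estimate or interval, and removes error bars from the mean plots on which the inference rests. This sits badly with 14.1.2 and with the estimation approach in 2.4.4.

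As to size, a 0.10 L gap between arms would arise by chance in roughly 7% to 49% of trials, depending on group size and SD. Every SD and the 0.10 L threshold are assumptions, and the calculation concerns the gap at 12 weeks, not the slope itself. The proposed interval would be wide, and no gain in precision over laboratory FVC is claimed. Its value is to limit what can be concluded. Severity is low: an inexpensive, optional improvement to an exploratory endpoint.

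**What to change.** 1. **Figures 9.18 and 9.19 (SAP 16.12.19).** Replace the instruction for no error bars with unadjusted mean ± SE, as in 14.1.2. Offset the arms or show bars at selected weeks for legibility.
2. **SAP 14.1.1 and 14.1.5, home FVC only.** Replace inference from figures with one pre-specified exploratory estimate. Take each participant's least-squares slope of weekly home FVC from baseline to Day 85, using the daily maximum as in Appendix 3 and a minimum number of readings fixed in advance (for example 6). Compare 300 mg with placebo using the Bayesian ANCOVA form and priors of 13.1.5, which already states: "The models will be adjusted for the following covariates: MMF use at day 1, baseline value and treatment". Baseline value here means baseline home FVC. Report the slope difference per 12 weeks with its 95% credible interval and P(>0), and the number of participants with too few readings.

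No change is needed for laboratory FVC.

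**Cost:** two figure edits, one ANCOVA and one table, on data already collected. **Downsides:** linearity to Day 85 is assumed, later readings are not used, self-measured values may be noisy, and unweighted slopes treat participants with few and many readings alike. The Day 85 cut-off and the minimum of 6 are proposals, not taken from the documents.

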14.1.2. Summary Measure

Summary statistics for all endpoints listed in Section 14.1.1 will be presented by visit and for the change from baseline at each visit. Line plots of unadjusted means \pm standard error at each visit and individual participant plots of the raw values will be presented by treatment groups and individual plot lines are differentiated by MMF use at Day 1 (solid line denote subjects on mycophenolate at day 1 and dashed line denote subjects not in mycophenolate at day 1). Information on positive autoantibodies is added to the subject ids in the legend as per Section 6.1.

14.1.3. Population of Interest

The efficacy analyses will be based on the "Per Protocol" analysis population, unless otherwise specified.

14.1.4. Strategy for Intercurrent (Post-Randomization) Events

Exploratory efficacy analysis will not account for intercurrent events (i.e. will adopt a 'while on treatment' strategy).

14.1.5. Statistical Analyses / Methods

Details of the planned displays are provided in Appendix 12 and will be based on GSK Data Standards and statistical principles.

201247

The endpoints / variables defined in Section 14.1.1 will be summarised using descriptive statistics, graphically presented (where appropriate) and listed.

Longitudinal model

Longitudinal Bayesian model as specified in Section 13.1.5 will be fitted for the change from baseline in the following endpoints:

- mRSS
- HAQ-DI
- Laboratory FVC (L)

The difference in the differences from baseline will be calculated across the treatment groups (GSK2330811 300mg – placebo).

Posterior means and equal tailed 95% credible intervals will be presented. In addition, except for Laboratory FVC, the probability the differences are <0 will be calculated and for Laboratory FVC, differences are >0 will be calculated. The line plots of the adjusted posterior mean change from baseline \pm credible intervals at each visit will be presented.

Non-Parametric Analysis

The CRISS endpoint is not expected to be normally distributed and so will be analysed using Bayesian non-parametric techniques including only placebo and GSK2330811 300mg arms.

Observed data from two groups are assumed to come from an underlying latent normal distributions with unit variance. Observations from these two latent normal distributions are generated from the truncated normal distributions in such a way to maintain the ordinality of the data. The parameter of interest is difference in the two latent means, δ . Prior distribution of δ , will be Cauchy distribution with shape parameter 0.5 and scale parameter $1/\sqrt{2}$. To obtain the posterior distribution for δ , analysis will follow the algorithm advocated by van Doorn, 2020.

Probability difference > 0 will be presented.

Boxplots of the predicted probability of improvement from baseline in the CRISS endpoints at day 85 and day 197 will be presented by treatment group.

Correlation Analysis

In addition, correlation analysis will be performed at Day 85 for set of endpoints listed below. The correlation will be presented as scatter plots of endpoints for each of the treatment groups, including the Pearson correlation coefficient. For ratios, correlations will use the log transformed data while the plot will present the untransformed data with the appropriate axis presented on the log scale.

- For each combination of change or ratio of key biomarkers
- Clinical endpoints vs biomarker endpoints for change or ratio (Following table lists the pair of endpoints to be plotted).

201247

	Endpoint 2				
Endpoint 1		Ratio/Change			
	1. CCL18 (Serum)	Ratio			
	2. Pro-C6 (Serum)				
	3. Disease Signature - GSVA Score (Upregulated	Change			
	and Downregulated)				
FVC (Change)	4. Lung Fibrosis Signature - GSVA Score				
	5. Cell Module Signature - GSVA Score (Fibrosis,				
	M1-Macrophage and M2-Macrophage)				
	1. Alpha SMA (Excluding Insufficient samples)	Ratio			
	2. COMP (Skin)				
	3. CCL2 (Skin)				
	4. PIIINP (Serum)				
	5. 2GSSc Skin Biomarker	Change			
	6. Disease Signature - GSVA Score (Upregulated				
mRSS	and Downregulated)				
(Change)	7. Cell Module Signature - GSVA Score (Fibrosis,				
	M1-Macrophage and M2-Macrophage)				
	1. Alpha SMA (Excluding Insufficient samples)	Ratio			
	2. CCL2 (Skin)				
Baseline OSM	3. PIIINP (Serum)				
(Skin)	4. 2GSSc Skin Biomarker	Change			
	5. mRSS				

Model checking and diagnostics will be carried out as described in Section 13.1.5.1.

201247

15. **REFERENCES**

Hanzelmann et al. (2013). GSVA: gene set variation analysis for microarray and RNA-seq data. BMC Bioinformatics, 14: p. 7.

J. van Doorn, A. Ly, M. Marsman & E.-J. Wagenmakers (2020): Bayesian rank based hypothesis testing for the rank sum test, the signed rank test, and Spearman's ρ , Journal of Applied Statistics. [DOI: 10.1080/02664763.2019.1709053]

Khanna et al. (2016) *The American College of Rheumatology Provisional Composite Response Index for Clinical Trials in Early Diffuse Cutaneous Systemic Sclerosis* Arthritis and Rheumatology, 68 (2), pp. 299-311.

Khanna et al. (2016b). Safety and efficacy of subcutaneous tocilizumab in adults with systemic sclerosis (Fascinate): a phase 2, randomised, controlled trial. Lancet, 387(10038): p. 2630-2640.

201247

